6.1.3 Unexpected AE or SAR

An AE or SAR is considered unexpected if the specificity or severity of it is not consistent with the applicable product information (e.g., Investigator's Brochure (IB) for an unapproved investigational product or package insert/summary of product characteristics for an approved product). Unexpected also refers to AEs or SARs that are mentioned in the IB as occurring with a class of drugs or as anticipated from the pharmacological properties of the drug, but are not specifically mentioned as occurring with the particular drug under investigation.

6.1.4 Serious AE or SAR

An AE or SAR is considered serious if, in the view of the sponsor-investigator, it results in any of the following outcomes:

- Death;
- Is life-threatening (places the subject at immediate risk of death from the event as it occurred);
- Requires inpatient hospitalization (>24 hours) or prolongation of existing hospitalization;
- Results in congenital anomaly/birth defect;
- Results in a persistent or significant incapacity or substantial disruption of the ability to conduct normal life functions;
- Important medical events that may not result in death, be life-threatening, or require hospitalization may be considered a serious adverse drug experience when, based upon appropriate medical judgment, they may jeopardize the patient or subject and may require medical or surgical intervention to prevent one of the outcomes listed in the definition. For reporting purposes, also consider the occurrences of pregnancy as an event which must be reported as an important medical event.

Pregnancy that occurs during the study must also be reported as an SAE.

6.2 Documentation of non-serious AEs or SARs

For non-serious AEs or SARs, documentation must begin from day 1 of study treatment and continue through the 30-day follow-up period after treatment is discontinued.

Collected information should be recorded in the Case Report Forms (CRF) for that patient. Please include a description of the event, its severity or toxicity grade, onset and resolved dates (if applicable), and the relationship to the study drug. Documentation should occur at least monthly.

6.3 SAEs or Serious SARs

6.3.1 Timing

After informed consent but prior to initiation of study medications, only SAEs caused by a protocol-mandated intervention will be collected (e.g. SAEs related to invasive procedures such as biopsies, medication washout).

For any other experience or condition that meets the definition of an SAE or a serious SAR, recording of the event must begin from day 1 of study treatment and continue through the 30 day follow-up period after treatment is discontinued.

6.3.2 Documentation and Notification

These events (SAEs or Serious SARs) must be recorded within 24 hours of learning of its occurrence.

6.3.3 Reporting

IRB Reporting Requirements:

The UNC-IRB will be notified of all SAEs that qualify as an Unanticipated Problem as per the UNC IRB Policies using the IRB's web-based reporting system within 7 days of the Investigator becoming aware of the problem.

Pregnancy

Pregnancies and suspected pregnancies (including a positive pregnancy test regardless of age or disease state) of a female subject occurring while the subject is on study should be recorded as SAEs. The patient is to be discontinued immediately from the study. The female subject should be referred to an obstetrician-gynecologist, preferably one experienced in reproductive toxicity for further evaluation and counseling.

The Investigator will follow the female subject until completion of the pregnancy, and must document the outcome of the pregnancy (either normal or abnormal outcome). If the outcome of the pregnancy was abnormal (e.g., spontaneous or therapeutic abortion), the Investigator should report the abnormal outcome as an AE. If the abnormal outcome meets any of the serious criteria, it must be reported as an SAE.

Funding Source (e.g. Manufacturer) Reporting Requirements:

If an investigator deems that an event is both a serious SAR AND unexpected, it must also (in addition to REDCap) be recorded on the MedWatch Form 3500A as per 21 CFR 312.32. The MedWatch 3500a form can be accessed at:

<http://www.fda.gov/Safety/MedWatch/HowToReport/DownloadForms/default.htm>.

(Please be sure and access form 3500a, and not form 3500). The Sponsor-investigator of the study will make the final determination regarding FDA submission.

Once the UNC Principal Investigator determines an event is a serious SAR AND unexpected, the MedWatch 3500A form will be submitted to the FDA.

7. Data and Safety Monitoring Plan

The Principal Investigator will provide continuous monitoring of patient safety in this trial with periodic reporting to an independent Medical Monitor. The medical monitor will review any reported Unanticipated Adverse Drug Effects after patients 5 and 10.

Meetings/teleconferences will be held at a frequency dependent on study accrual, and in consultation with the study Biostatistician. These meetings will include the investigators and any other relevant personnel the principal investigators may deem appropriate. At these meetings, the research team will discuss all issues relevant to study progress, including enrollment, safety, regulatory, data collection, etc.

The team will produce summaries or minutes of these meetings. These summaries will be available for inspection when requested by any of the regulatory bodies charged with the safety of human subjects and the integrity of data including, but not limited to, the oversight (Office of Human Research Ethics (OHRE) Biomedical IRB, the Scientific Review Committee (SRC), the Office of Clinical Trials (OCT), or the North Carolina TraCS Institute Data and Safety Monitoring Board (DSMB).

The PI will be responsible for submitting the following information for review by the independent medical monitor: 1) safety and accrual data including the number of study participants imaged; 2) significant developments reported in the literature that may affect the safety of participants or the ethics of the study; 3) preliminary response data; and 4) summaries of team meetings that have occurred since the last report. Findings of the medical monitor review will be disseminated by memo.

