4. STUDY PROCEDURES

Patients with suspected (but not confirmed) endometriosis and suspicion of extragenital DIE who are scheduled for planned operative laparoscopy with no hormone treatment for at least two cycles will be recruited from the Minimally Invasive Gynecological Surgery Clinic (Director, [name], Co-I) at UNC. If women are amenorrhoeic, 56 days will be used as a substitute for 2 cycles. The Endometriosis Health Profile-30 (EHP-30), a quality of life questionnaire used in women with endometriosis, a pain numeric rating scale, and information about the last menstrual period will be obtained. Patients will undergo FES PET/MR within 4 weeks prior to surgery. Prior to surgery, suspected areas of endometriosis will be identified on imaging. These imaging findings will then be

compared to surgical findings and histopathology from exploratory laparotomy. Surgical documentation of endometriosis location will rely on published, consensus staging methods.^{15,16} Surgeons will not see the results from the FES-PET/MRI prior to surgery. The results of FES-PET MRI will not be used to guide surgery. The surgeons will be performing exploratory laparoscopy as per standard of care.

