4.2 Research Imaging Procedure

Participants who consent for the study will be escorted by the research coordinator to the dedicated study room for the imaging exam. For our female patients who are of child bearing age, a pregnancy test will be performed prior to the administration of the radiotracer.

The subject will have the PET-MR scan performed in a similar manner to a conventional clinical PET-MR scans. The imaging agent will be injected approximately one hour prior to imaging after dosimetry and radiotracer has been verified per protocol. The research technologist will assist in positioning the patient in the PET-MR unit. Once positioned, the total scan time is approximately 1 hour. The length of time for the positioning and examination of a subject's pelvis may vary but it is expected that the entire visit will take about 150 minutes. We will not utilize gadolinium contrast agent for this study.

We have extensive experience in the synthesis of radiotracers at the UNC Biomedical Research Imaging Center (BRIC), with dedicated radiochemists and radiopharmacists. We thus expect to be able to synthesize the radiotracer without much difficulty, as there is an established IND available for cross-filing on the NCI website¹⁷, which contains a

full set of manufacturing and QC documents. A manufacturing IND has already been obtained.

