4.3 Follow-Up Phone Call

Patients will be called 3 to 4 weeks following the FES PET scan to determine the last menstrual period following the scan.

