4.4 Medical Record Abstraction

Participants' medical record will be reviewed for up to 3 months following their initial research imaging to meet the primary aim. The operative surgeon will be asked to fill out a specific post-operative form defining the areas in which they identified visible endometriosis within the pelvis.

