11.3 Toxicity of FES in humans

Estradiol is a naturally occurring substance with biochemical and pharmacologic properties nearly identical to FES. It is important to interpret toxicity data for FES relative to reported toxicity for estradiol in the context of the intended use of FES as a single-dose-administration agent for diagnostic imaging. In this setting, FES reaches physiologic levels (i.e., greater than post-menopausal levels) only on a transient basis. This must be viewed in the context of many years of exposure to physiologic levels of estradiol in most women. [¹⁸F]FES could potentially exert toxic effects through one of three mechanisms: (1) radiation exposure to tissues from the radioactive label¹¹, (2) physiologic actions mediated through the ER, and (3) directly toxic or mutagenic effects of FES metabolites. Radiation exposure from [¹⁸F]FES at activity doses used in PET (6 mCi, typical) is low, and is comparable to other nuclear medicine procedures¹¹. Radiation exposure is discussed in detail in Section 10.4. With respect to the other two mechanisms of toxicity, FES injected as a bolus for PET imaging transiently reaches physiologic concentrations, but returns to sub-physiologic levels within an hour after injection. As such, toxic effects due to actions mediated through the ER and directly toxic effects of metabolites will be far less than those of natural ER ligands.

Given the biochemical and pharmacologic similarity between FES and estradiol, the low mass administered and short-term exposure to FES resulting from PET studies, the estradiol toxicity literature serves as an appropriate gauge for any potential toxicity of FES.

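### The pregnancy rule in 6.3.3 also discontinues women who have already had their only FES scan, which prevents no exposure and can stop collection of primary-aim data

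*Combined protocol and SAP*

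**What the plan says.** The pregnancy paragraph of 6.3.3 covers "Pregnancies and suspected pregnancies (including a positive pregnancy test regardless of age or disease state) of a female subject" arising while she is on study. It makes them SAEs and then orders: "The patient is to be discontinued immediately from the study". It does not separate the time before the scan from the time after it, and suspicion alone is enough. One kind of follow-up continues: "The Investigator will follow the female subject until completion of the pregnancy, and must document the outcome of the pregnancy".

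The rest of the protocol fixes the timing:

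- **Exposure.** Section 4.2 describes one injection for one PET/MR visit without gadolinium, and says "a pregnancy test will be performed prior to the administration of the radiotracer". Section 11.3 refers to "the intended use of FES as a single-dose-administration agent for diagnostic imaging".
- **Surgery.** Section 4: "Patients will undergo FES PET/MR within 4 weeks prior to surgery". The laparoscopy is standard of care.
- **After the scan.** Section 4.3: "Patients will be called 3 to 4 weeks following the FES PET scan", to ask about the last menstrual period. Section 4.4 adds a surgeon's post-operative form and says that the "medical record will be reviewed for up to 3 months following their initial research imaging to meet the primary aim". Section 3.2 also sets follow-up at up to 3 months after imaging.
- **Analysis.** Section 5.1 defines diagnostic accuracy by histology and by symptomatic improvement within 3 months of surgery. Section 5.2 computes sensitivity and specificity against surgical findings and histopathology. It recruits until 12 women have been imaged, and replaces only those who do not complete PET/MR.

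**The concern.** A discontinuation rule for pregnancy normally protects a fetus from further exposure. Here the only exposure is one injection, so after the scan the rule has nothing left to prevent. What remains for a scanned woman is observation: telephone calls, a form completed by the surgeon, and review of records from standard care.

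The rule could realistically be triggered. Participants are of childbearing age, have had no hormone treatment for at least two cycles, and are asked about their last period 3 to 4 weeks after the scan. No sentence readmits a woman whose suspected pregnancy is ruled out. Section 8.4 requires the study to be run exactly as written except in an emergency, so staff who went on abstracting the record of a discontinued subject would be departing from the protocol.

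At stake is the reference standard, or part of it, for a woman who has already had the tracer and counts toward the 12.

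**Working it through.** The plan gives no figure for this point, so the check sets the rules against the schedule and then sizes the loss of one woman.

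**1. Does the rule reach scanned women?** Yes. It applies while the subject is on study, and 3.2 follows subjects for up to 3 months after imaging. The phrase is not defined, and 6.3.1 limits SAE recording to day 1 through a 30-day follow-up, so a shorter window of about 30 days is arguable. Surgery falls within 4 weeks = 28 days of the scan, and 28 < 30. Both readings therefore cover the whole interval from scan to surgery. They differ only for pregnancies found later.

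**2. What exposure remains after the scan?** None. There is one injection, no contrast agent and no second scan described.

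**3. What does the rule stop, read literally?**

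| Pregnancy found or suspected | Already in hand | Stopped | Effect on analysis |
|---|---|---|---|
| Before injection | Baseline questionnaires | Scan and everything after | Screen failure, replaced under 5.2 |
| After scan, before surgery | Questionnaires, scan, SUV | Call if not yet made, surgeon's form, histology, record review | 12 − 1 = 11 of 12 with a reference standard, if hers is not collected |
| After surgery | The above plus surgical and histology findings | Rest of record review; call if not yet made | 12 of 12 in the 5.2 comparison; at least 11 of 12 with the full 5.1 reference |

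The study's own call can raise the suspicion before surgery. The earliest call is day 21 and the latest surgery day 28, so the call can come up to 28 − 21 = 7 days before surgery.

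**4. How large is one lost reference standard?** Each woman is 1/12 = 8.3% of those scanned. Section 5.2 plans 95% intervals but does not name the method, so I assume the exact (Clopper-Pearson) interval. When all n histology-positive women are detected, its lower limit is 0.025^(1/n).

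| Positives, before → after loss | Lower limit before | Lower limit after | Fall |
|---|---|---|---|
| 12 → 11 | 0.025^(1/12) = 73.5% | 0.025^(1/11) = 71.5% | about 2 points |
| 8 → 7 (assumption) | 0.025^(1/8) = 63.1% | 0.025^(1/7) = 59.0% | about 4 points |

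The documents do not give the number of histology-positive women, so 8 to 12 is an assumed range. A histology-negative woman would cost precision in specificity instead. The documents give no pregnancy rate, so no expected number of losses can be derived.

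**The case against.** The strongest case against is that the loss is inferred. The sentence says that the woman is discontinued. It does not say that her data are deleted or that she leaves the analysis, and 5.2 counts women who completed imaging, as she did. Her operation and pathology report come from standard care whatever her study status. A reader might infer that the rule strips a scanned woman's results from the study, or ends all follow-up. The documents support neither: nothing discards collected data, and 6.3.3 keeps following her to the end of the pregnancy. Her scan, SUV, EHP-30 and pain score are in hand, so Aim 3 is largely unaffected. What stands is narrower. Pregnancy follow-up covers the pregnancy outcome only, and no sentence allows the remaining study data to be collected after discontinuation.

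Second, symptomatic improvement is named in 5.1 but enters no calculation in 5.2, so a pregnancy found after surgery has almost no analytic effect. This is correct.

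Third, a real pregnancy before surgery may postpone the laparoscopy, and the reference standard is then lost under any wording. This is also correct, and it confines the avoidable loss to refuted suspicions and operations that go ahead.

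Fourth, the falls in the lower limit would follow from losing any one positive woman for any reason. They show the size of one loss and say nothing about how often this rule would cause one.

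**Conclusion.** The concern holds in a limited form. The discontinuation sentence reaches women already scanned, prevents no study exposure in them, and, followed literally, stops data collection that serves the primary aim for a woman who is not replaced.

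The effect depends on timing. After surgery, the 5.2 comparison is complete and only the 5.1 symptom component is at risk. Between scan and surgery, a reference standard is avoidably lost only if the suspicion is refuted or surgery still takes place. One such loss costs about 2 to 4 points on the exact lower limit for sensitivity. That figure assumes that she is histology-positive, that every positive woman is detected, and that 8 to 12 women are positive.

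A reader might take the 2 to 4 points as the expected cost of the rule. The documents give no event rate, so they do not support that. Severity is minor, and the change is a cheap improvement.

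**What to change.** Limit the discontinuation sentence in 6.3.3 to pregnancy found or suspected before FES injection, and add:

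> Subjects already scanned, with their continued agreement, remain in study follow-up and analysis, and their scan, surgical, histology and 3-month data continue to be collected and used.

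Leave SAE recording, referral and pregnancy-outcome follow-up as they are. No new screen-failure rule is needed, because 5.2 already covers women who are not scanned.

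The cost is a written amendment with IRB approval before use (8.7) and a record of the woman's continued agreement. No visit, test or imaging is added. The change does not recover a reference standard when surgery is postponed.

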7.1 Adverse Events Safety Assessments

A licensed provider will observe subject vitals following the administration of the radiotracer on through the completion of the imagining scan. Study personnel will contact subjects 1 day (+3 days window) after to inquire about delayed onset complications. The subjects will also be given a phone number that they can call to reach a nurse if they believe they have developed a complication of the procedure.

8. STUDY MANAGEMENT

8.1 Institutional Review Board (IRB) Approval and Consent

It is expected that the IRB will have the proper representation and function in accordance with federally mandated regulations. The IRB should approve the consent form, assent form, and protocol.

In obtaining and documenting informed consent, the investigator should comply with the applicable regulatory requirement(s), and should adhere to Good Clinical Practice (GCP) and to ethical principles that have their origin in the Declaration of Helsinki.

Before recruitment and enrollment onto this study, the patient will be given a full explanation of the study and will be given the opportunity to review the consent form. Each consent form must include all the relevant elements currently required by the FDA Regulations and local or state regulations. Once this essential information has been provided to the patient and the investigator is assured that the patient understands the implications of participating in the study, the patient will be asked to give consent to participate in the study by signing an IRB-approved consent form.

Prior to a patient's participation in the trial, the written informed consent form should be signed and personally dated by the patient and by the person who conducted the informed consent discussion.

For patients under the age of 18, appropriate assent must be obtained in addition to parental permission prior to participation in the study.

8.2 Registration Procedures

Study participants will be registered into CRMS, a web based clinical research platform by one of the Study Coordinators.

8.3 Data Management and Monitoring/Auditing

The FES PET-MR scan that is obtained of all eligible enrolled subjects will be de-identified for inclusion in the appropriate readers study. Copies of the clinical report forms as well as the de-identified images described in the preceding will be submitted for each case to the Study Coordinators for maintaining the study record and entering data in preparation for the reader study.

The online REDCap software system provided by UNC's TraCS Institute will be used to collect and store research data. Information regarding why a data value is missing will be documented in the study database.

Coded copies of subject study images will be received at the time of the scan and will be stored in the participant file in a locked file cabinet.

8.4 Adherence to the Protocol

Except for an emergency situation in which proper care for the protection, safety, and well-being of the study patient requires alternative treatment, the study shall be conducted exactly as described in the approved protocol.

8.5 Emergency Modifications

UNC investigators may implement a deviation from, or a change of, the protocol to eliminate an immediate hazard(s) to trial subjects without prior UNC's IRB/IEC approval/favorable opinion.

For any such emergency modification implemented, an IRB modification form must be completed by UNC Research Personnel within five (5) business days of making the change.

8.6 Protocol Deviations/Violations

According to UNC's IRB, a protocol deviation is any unplanned variance from an IRB approved protocol that:

- Is generally noted or recognized after it occurs
- Has no substantive effect on the risks to research participants
- Has no substantive effect on the scientific integrity of the research plan or the value of the data collected
- Did not result from willful or knowing misconduct on the part of the investigator(s).

An unplanned protocol variance is considered a violation if the variance meets any of the following criteria:

- Has harmed or increased the risk of harm to one or more research participants.
- Has damaged the scientific integrity of the data collected for the study.
- Results from willful or knowing misconduct on the part of the investigator(s).
- Demonstrates serious or continuing noncompliance with federal regulations, State laws, or University policies.

If a deviation or violation occurs please follow the guidelines below:

Protocol Deviations: UNC personnel will record the deviation and report to any data and safety monitoring committee in accordance with their policies. Deviations should be summarized and reported to the IRB according to the UNC IRB reporting requirements.

Protocol Violations: Violations should be reported by UNC personnel within one (1) week of the investigator becoming aware of the event using the same IRB online mechanism used to report Unanticipated Problems.

Unanticipated Problems:

Any events that meet the criteria for "Unanticipated Problems" as defined by UNC's IRB must be reported by the study team using the IRB's web-based reporting system.

